- a) Gingival inflammation (MGI)

Secondary analyses were the comparison of data with respect to product effectiveness:

- a) Reduction in bleeding on probing (BOP) and Turesky modification of the Quigley-Hein Plaque Index (PI) grading on all natural teeth in the dentition

The primary statistical analytic framework was the repeated measures analysis of variance on three primary outcomes: probing depth, gingival index, and plaque. The primary hypothesis tested was the treatment by time interaction, i.e., did one treatment work better during the observations of these three outcomes? In other words, not just the total change, but also the rate of that change might differ between treatments. The proposed analysis was based on data that were generally normally distributed and similarly. If not, data transformations or link functions were used.

Outcomes

Raw data were collected from examinations of each tooth with regard to probing depth, gingival index, and plaque. Data were collected over three time periods, recorded into patient files, and transferred to Excel Workbooks, with one Workbook per patient. Each Workbook contained three tabs, one for each visit.

The raw data were combined as two levels of indexes for the three measures. The first outcome was a global score index of probing depth, gingival index, and plaque measurement. The global index was derived from individual tooth scores for each measure divided by the number of teeth measured. The second index derived from the same raw data described the three measures in terms of average scores for implant and non-implant teeth.

For the second analysis, implanted tooth data were separated from normal teeth data within each patient. Implant scores for each patient were averaged for probing depth, gingival index, and plaque scores. If a patient had one implant, each score was identical to the single measurement. With more than one implant, a single implant score for each patient was derived from averaging each of the three measures over the three observation periods. Likewise for each patient, the non-implanted teeth measures were averaged for each of the three times of assessment.

Individual patient data of the averages of the implant and non-implant teeth were calculated for each time period and transferred to a master data sheet.

Data Management and Statistical Analysis

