From raw data of individual teeth, each patient received a global index of periodontal disease, gingival index, and plaque for each visit. The global index for each of these measurements was found by dividing the sums of patient probing depth, gingival index, and plaque findings collected for each tooth by the number of teeth assessed. Over the three assessment periods, global scores of probing depth, gingival index, and plaque were collected for the first and last visits with probing depth scores not collected during the second visit. These outcomes are measured as individual slopes of responses across the three observation visits. The slope represents the rate of change.

The overall view of the response of each measure to the treatment group is summarized in the following general linear model Table 2. Table 3 shows the cell statistics for the slopes of each condition and outcomes reported in Table 2.

Table 2. Master table of variance components attributable to treatment on individual rates of change on the three measures: probing depth, gingival index, and plaque.

Source	Variable	Type III SS	df	MS	F	Sig.
Group	Slope of probing depth, time 1 to 3	0.125	1	0.125	1.191	0.28
	Slope of gingivitis index, time 1 to 3	0.485	1	0.485	11.748	0.001
	Slope of plaque score, time 1 to 3	4.019	1	4.019	69.751	0.000
Error	Slope of probing depth, time 1 to 3	5.75	55	0.105		
	Slope of gingivitis index, time 1 to 3	2.27	55	0.041		
	Slope of plaque score, time 1 to 3	3.169	55	0.058		
Total	Slope of probing depth, time 1 to 3	6.519	57			

Slope of gingivitis index, time 1 to 3	6.135	57
Slope of plaque score, time 1 to 3	18.861	57
Corrected Total	Slope of probing depth, time 1 to 3	5.875
	Slope of gingivitis index, time 1 to 3	2.755
	Slope of plaque score, time 1 to 3	7.187
	R Squared = .021 (Adjusted R Squared = .003)	
	R Squared = .176 (Adjusted R Squared = .161)	
	R Squared = .559 (Adjusted R Squared = .551)	

Table 3. Details of cell statistics for analysis described in Table 2.

Descriptive Statistics					
	N	Minimum	Maximum	Mean	Std. Deviation
Probing depth at time 1	57	2.04	4.63	2.71614	0.432843
Probing depth at time 3	57	0	4.42	2.50351	0.804056
Gingivitis index at time 1	57	1.41	2.23	1.97158	0.172065
Gingivitis index at time 2	57	0	2	1.71754	0.364095
Gingivitis index at time 3	57	0	1.92	1.48456	0.451688
Plaque score at time 1	57	1.47	3.54	2.67895	0.555475
Plaque score at time 2	57	0	3.11	2.19614	0.596444
Plaque score at time 3	57	0	2.92	1.77386	0.618124

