The gingivitis index is based on the Gingival Index system,² in this case, the global gingival index is GGI. The GGI was also significantly higher for the test group (Group X) at the initial visit; for the test group (Group X) = 2.03 (0.025) and GGI for the control group (Group A) = 1.91 (0.035), ($t = -2.89$, $df = 55$, $p = 0.006$). Figure 6 illustrates a potential interaction between treatment and time of observation that required statistical consideration and control. Again, GGI for visit 1 was used as a covariate so as not to over-estimate treatment effects on GGI represented in a time-by-treatment interaction. The ANCOVA upheld a statistically significant ($t = 2.12$, $df = 51$, $p = 0.039$) between treatments. Boxplots of the GGI across visits is shown in Figure 7. The test group (Group X) reduction in GGI was 27.3% versus the control group's (Group A) reduction of 20.4%, also statistically significant difference by repeated measures analysis of variance ($F = 8.141$, $df = 1$, $p = 0.0046$).

[figure not shown]

Figure 6. Interaction plot showing group assignment interacting with time on gingival index measures (GGI).

[figure not shown]

Figure 7. Boxplots of gingival index measures comparing treatment control group (Group A) and test group (Group X). Test group (Group X) started with higher gingival index levels. Gingival index decreased more and faster in test group (Group X) than in the control group (Group A), though both decreased significantly.

Differential Effects of Mouthwashes on Implants in Control Group (Group A) and Test Group (Group X)

Of particular interest was the specific effect that control mouthwash (rinse A) and test mouthwash (rinse X) might have on implant and non-implant sites across the three outcomes. Table 4 illustrates the overall study results of treatments and implants on the three outcomes. Probing depth was not different between treatments for implant and non-implant sites. Plaque and gingival indexes were improved significantly under test rinse Treatment (rinse X), with details described in Tables 5, 6, and 7 below. In addition, implant sites improved at a faster rate under test rinse Treatment (rinse X) conditions for both gingivitis and plaque.

Table 4. Omnibus test for main effects and interactions of control mouthwash (rinse A) and test mouthwash (rinse X) on implant and non-implant sites.

Sites of Implants responding differently to treatment					
All outcomes: measures in table					

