There is a clear advantage to using ClōSYS® Ultra Sensitive oral rinse treatment (test rinse X) in terms of plaque and gingival index. In addition, ClōSYS® Ultra Sensitive oral rinse (test rinse X) appeared to have a preferential benefit for implant sites, over both control treatment (placebo rinse A) and over non-implant sites. The ClōSYS® Ultra Sensitive rinse (test rinse X) significantly reduced the plaque index and gingival index as compared to initial measures and those in control group (placebo rinse A) ($p < 0.001$). The observation of higher initial gingivitis scores for the ClōSYS® Ultra Sensitive oral rinse (test rinse X) did not affect the superiority of this test group treatment. In controlling for the inequality at baseline, and analysis of covariance showed the reduction of the plaque score remained significantly better in the ClōSYS® Ultra Sensitive oral rinse group (test rinse X) than for the control group (placebo rinse A) ($p < 0.001$). Also, using pre-post difference scores and slopes of the scores over time showed the treatment effect to be robust to the mismatch of initial levels of gingivitis and plaque ($P < 0.001$ for both).

Both groups improved from the use of mouthwashes, but the ClōSYS® Ultra Sensitive oral rinse (test rinse X) improved more and at a faster rate ($p < 0.001$) compared to the control group (placebo rinse A). There was no apparent effect on periodontitis between the two intervals in which it was measured.

Implant sites were significantly more ($p < 0.001$) and faster ($p < 0.001$) improved in the ClōSYS® Ultra Sensitive oral rinse group (test rinse X) than the other non-implanted teeth and in the control group (placebo rinse A).

Both ClōSYS® Ultra Sensitive oral rinse (test rinse X) and placebo rinse (rinse A) tested are safe to oral tissues and did not show any adverse effects.

Both ClōSYS® Ultra Sensitive oral rinse (test rinse X) and placebo rinse (rinse A) tested are safe to oral tissues and do not have any adverse effects.

Signature Page

[name]

Principal Investigator

[name] [name], PhD

REFERENCES

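### The MGI result printed as global (27.3% v 20.4%, p = 0.0046) does not follow from the global data in Tables 2 and 3, and the Conclusions omit the baseline-adjusted p = 0.039

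*Combined protocol and SAP*

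**What the plan says.** Section 11 (Statistical Evaluation) lists one measure under the primary objective: "a) Gingival inflammation (MGI"). The next paragraph names three primary outcomes (probing depth, gingival index, plaque) and makes the treatment-by-time interaction in a repeated-measures analysis the primary hypothesis.

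Global MGI is then tested in four places:

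- **Table 2** (Global Score Analyses): group effect on the MGI slope, F = 11.748 on 1 and 55 df, Sig. 0.001.
- **Global Gingival Index Score, adjusted test:** baseline means differed, "for the test group (Group X) = 2.03 (0.025) and GGI for the control group (Group A) = 1.91 (0.035"), p = 0.006. Baseline was therefore made a covariate to avoid overstating the effect, giving t = 2.12, df = 51, p = 0.039.
- **Same section, headline figures:** the test group's "reduction in GGI was 27.3% versus the control group's (Group A) reduction of 20.4" per cent, with a repeated-measures F = 8.141, df = 1, p = 0.0046. The error df is not printed.
- **Conclusions:** difference scores and slopes "showed the treatment effect to be robust to the mismatch of initial levels of gingivitis and plaque", with P < 0.001 stated for both. The covariance analysis is cited for plaque only.

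**The concern.** The percentages, the p-value beside them and the p-value in the Conclusions appear to come from different analyses, with nothing to say which dataset produced which. A reader cannot tell how large the MGI effect is. The adjusted analysis, which the document itself says was needed because the arms differed at baseline, gives the weakest result. It is absent from the Conclusions, although they claim robustness to that very imbalance.

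**Working it through.** **Inputs.** Table 3 (N = 57): MGI mean 1.97158 at time 1 and 1.48456 at time 3 (SD 0.451688, minimum 0); mean slope −0.24351, minimum −0.99. Table 2: group SS 0.485, error SS 2.27 on 55 df, corrected total 2.755. Baselines by arm: 2.03 (test) and 1.91 (control). The arm split of the 57 is not printed. I assume 28 control and 29 test, which returns the Table 3 baseline: (28 × 1.91 + 29 × 2.03)/57 = 1.971.

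**1. The tables are coherent.** Slope = (time 3 − time 1)/2 = (1.48456 − 1.97158)/2 = −0.24351, as printed. R² = 0.485/2.755 = 0.176, as printed.

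**2. Arm reductions from Tables 2 and 3.**
- Slope difference = √[0.485 × (1/28 + 1/29)] = 0.1845.
- Control slope = −0.24351 + 0.1845 × 29/57 = −0.150. Test slope = −0.24351 − 0.1845 × 28/57 = −0.334.
- Change is twice the slope: −0.299 and −0.668.
- Reductions: 0.299/1.91 = **15.7%** (control) and 0.668/2.03 = **32.9%** (test).
- Splits from 27/30 to 30/27 give 15.3–16.3% and 32.6–33.6%.

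The same method recovers the other outcomes. Plaque changes come out at −0.365 and −1.427 (printed 0.365, sign missing, and −1.43). Probing depth changes come out at −0.117 and −0.305 (printed means give −0.12 and −0.31).

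**3. In reverse.** The printed pair implies changes of 0.273 × 2.03 = 0.554 and 0.204 × 1.91 = 0.390, so a slope difference of 0.082. Then SS = 0.0823² × (28 × 29/57) = 0.096, against 0.485 in Table 2. F would be 2.3 (error SS held) or 2.0 (corrected total held), with p about 0.13 to 0.16, not 11.748.

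**4. Zero scores.** That zeros stand for missing visits is an inference. The time-3 mean and SD allow at most four zeros, since a fifth makes the remaining variance negative. A patient who ends at zero has a 100% reduction, so removing one always lowers that arm's figure. Control therefore falls from 15.7% and never reaches 20.4%. Removing one control and three test zeros (assumed) gives final means of 1.611 × 28/27 = 1.671 and 1.362 × 29/26 = 1.519, hence 12.5% and 25.2%.

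**5. A likely source.** Table 5 is titled probing depth but its measure is labelled GGI. Its 102 error df fit 106 site averages: 53 patients × 2 site types, in cells of 27, 27, 26 and 26. For a linear contrast over three visits, each effect in index points is √(2 × SS × 0.1510)/4, where 0.1510 = 2/27 + 2/26.
- Time 0.534, site 0.169, group 0.133. The three-way term is 0.004 and is ignored.
- Drops: test implants 0.836, test teeth 0.499, control implants 0.569, control teeth 0.232. Implants and Gingival Index prints these as 83%, 50%, 57% and 23%, which supports the decoding and shows index points presented as percentages.
- Over Table 1 baselines, control: (0.569 + 0.232)/(2.06 + 1.87) = **20.4%**. Test: (0.836 + 0.499)/(2.82 + 2.01) = **27.6%**, against 27.3% printed.

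**6. p-values.** F = 8.141 gives p = 0.0061 on 55 df, 0.0049 on 169 df and 0.0046 on 312 df. Printed to four decimals, 0.0046 needs roughly 280 to 400 error df. The global data hold 57 × 3 = 171 patient-visits. The site data hold 106 × 3 = 318 rows, and 318 − 6 group-by-visit cells = 312. Table 2's F = 11.748 on 1 and 55 df gives p = 0.00116. The adjusted t = 2.12 on 51 df gives 0.039, as printed.

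**The case against.** A reader might infer that 27.3% v 20.4% cannot be produced from the trial's data, or that about 300 error df is impossible. The documents do not support either. Step 5 gives control exactly and test within 0.3 points, and 318 site-visit rows account for the p-value. What stands is that a probable site-level result is presented as the global one, with a p-value that counts visits and sites from one patient as independent.

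A reader might also infer that P < 0.001 for gingivitis is baseless and should simply be struck out. That goes too far. Table 5's time-by-group test has F = 35.047; even halving F and df (17.5 on 51) leaves p about 0.0001. With one control and three test zeros removed, each slope taken as −0.99, the patient-level slope test has error SS about 0.10 and F about 134. With zeros kept, the conflict is narrow: 0.00116 against < 0.001. The 0.039 is also a different test from the one the Conclusions cite, and it is printed openly in the results.

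Nor is benefit inflated by the percentages. The printed gap of 6.9 points is smaller than the 17.3 points from Tables 2 and 3 or the 12.7 without zeros, and the Conclusions do not quote it. Making covariance analysis the sole primary test would be a preference, since Section 11 names the treatment-by-time interaction.

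These points limit the finding but do not remove it. The section still attaches figures to the global index that its own tables contradict, and the Conclusions still leave out the adjusted MGI result.

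**Conclusion.** The point holds as a mislabelled and unreconciled primary result. Tables 2 and 3 imply about 33% v 16% for global MGI where the text prints 27.3% v 20.4%, and the control figure is out of reach with or without zeros. The p = 0.0046 reflects about 300 error df; patient-level df give 0.0061. The Conclusions' P < 0.001 does not match Table 2's 0.00116, and the adjusted p = 0.039 is missing.

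This rests on an assumed arm split (the result barely moves across the splits tried), an assumed zero allocation for the 25% v 12% variant, and an inferred site-level source. An unreported model-based percentage cannot be excluded, though the text presents plain reductions. It would be wrong to conclude that the effect disappears: every test of global MGI discussed here favours the test rinse at p < 0.05.

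**What to change.** 1. Reconcile the analysed patients: 53 in Table 1, 54 randomised (and implied by 51 df with one covariate), 56 in the implant count, 57 in Tables 2 and 3. State what the zero scores are and how they are handled.
2. Recompute the global MGI reductions from that one patient-level dataset, or relabel 27.3% v 20.4% as site-averaged if that is confirmed as their source.
3. Replace p = 0.0046 with a test whose error df reflects patients, and print the df.
4. In the Conclusions, give the baseline-adjusted Day 90 MGI difference with 95% CI, p and error df (currently p = 0.039) beside the treatment-by-time test.
5. Replace P < 0.001 for gingivitis with the recomputed value, whichever way it moves.

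The cost is a re-run on existing data. The adjusted p-value quoted may be less favourable than the present wording.

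### The repeated measures ANOVA quoted for the primary outcome (global MGI: F = 8.141, df = 1, p = 0.0046) does not fit the global MGI data or Table 2, and the documents do not show where it comes from

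*Combined protocol and SAP*

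**What the plan says.** Section [11], Statistical Evaluation, ties the primary objective to "Gingival inflammation (MGI"). It then sets the method: "The primary statistical analytic framework was the repeated measures analysis of variance on three primary outcomes: probing depth, gingival index, and plaque". It also says which effect matters: "The primary hypothesis tested was the treatment by time interaction", and explains that the rate of change is of interest as well as the total change.

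On the data, section [11] states "Data were collected over three time periods", and Global Score Analyses says that "each patient received a global index of periodontal disease, gingival index, and plaque for each visit". Table 3 gives N = 57 for the gingivitis index at each of times 1, 2 and 3.

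Three between-group results on change in global MGI are reported:

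- Table 2, row "Slope of gingivitis index, time 1 to 3": F = 11.748 on 1 and 55 df, significance 0.001.
- Global Gingival Index Score, ANCOVA with the first visit as covariate: t = 2.12, df = 51, p = 0.039.
- The same paragraph, attached to reductions of 27.3% (test) and 20.4% (control): "also statistically significant difference by repeated measures analysis of variance", with F = 8.141, df = 1, p = 0.0046.

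**The concern.** The third result carries the name of the planned primary framework and is applied to the primary outcome, so a reader will take it as the planned test. It cannot be checked directly, because the error df, the effect tested (group, time or their interaction) and the data file are all missing. It can be checked indirectly: F, the numerator df and p together determine the error df. If the implied error df exceeds what the data can supply, at least one printed figure is wrong or the model was fitted to something other than the global MGI scores.

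At stake is which figure describes the evidence on the primary outcome. The three results run from p = 0.001 to p = 0.039, and the one labelled as the planned method is the one that cannot be traced.

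**Working it through.** **Inputs.** F = 8.141, df = 1, p = 0.0046 (Global Gingival Index Score). N = 57 at three assessments (Table 3). MGI slope row of Table 2: group SS 0.485 on 1 df, error SS 2.27 on 55 df, F = 11.748. Mean global MGI 1.97158 at time 1 and 1.48456 at time 3; mean slope -0.24351 (Table 3). Baseline global MGI 1.91 (control) and 2.03 (test).

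**Step 1. Check the method on neighbouring results.**
- Table 2: 0.485 / (2.27 / 55) = 11.75, and the upper tail of F(1, 55) at 11.748 is 0.0012. Printed: 11.748 and 0.001.
- ANCOVA: two-sided p for t = 2.12 on 51 df is 0.0389. Printed: 0.039.

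Both reproduce.

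**Step 2. Evaluate the quoted result.** p = P(F(1, d) > 8.141):

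| Error df d | What it would represent | p |
|---|---|---|
| 55 | between patients, or the 1-df slope contrast (57 - 2) | 0.0061 |
| 110 | within patients, three assessments (55 x 2) | 0.0052 |
| 165 to 171 | all 57 x 3 = 171 MGI values treated as independent | 0.0049 |
| 314 | for comparison | 0.0046 |
| 330 | for comparison | 0.0046 |
| chi-square limit | Wald test | 0.0043 |

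Solving for d: p lies in [0.00455, 0.00465) only for d from 281 to 404. If p was truncated rather than rounded, the range is 244 to 330. Both ranges exceed 171. With 2 numerator df, F(2, 110) gives 0.0005. A sphericity correction lowers the df and raises p, which moves further from 0.0046.

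**Step 3. Compare with Table 2.** (1.48456 - 1.97158) / 2 = -0.24351, exactly the mean slope in Table 3. The slope is therefore half the change from the first to the last assessment, and the group test on it is the 1-df treatment-by-time contrast between those assessments. On 57 patients that contrast is F(1, 55) = 11.748, not 8.141.

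**Step 4. Compare with the percentages in the same sentence.** The arm split of the 57 is not stated; I assume control/test splits from 27/30 to 30/27, with the larger fall in the test group.
- From Table 2, the slope difference is sqrt(0.485 / (n1 x n2 / 57)). For 28/29 this is sqrt(0.485 / 14.246) = 0.1845. The control slope is -0.24351 + 0.1845 x 29/57 = -0.150, a fall of 2 x 0.150 / 1.91 = 15.7%. The test slope is -0.24351 - 0.1845 x 28/57 = -0.334, a fall of 2 x 0.334 / 2.03 = 32.9%. Over the assumed splits the range is 15.3% to 16.3% against 32.6% to 33.6%.
- In reverse, 27.3% of 2.03 less 20.4% of 1.91, halved, is a slope difference of 0.0823. With Table 2's error, F = 14.246 x 0.0823² / (2.27 / 55) = 2.3, p about 0.13.

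The percentages and Table 2 do not describe the same change.

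**The case against.** **The single numerator df proves nothing.** This stands. A test across three assessments with time as a category has 2 df, but section [11] speaks of rate of change and Global Score Analyses works with slopes. A linear-time contrast has 1 df, and the plan does not require categorical time.

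**A misprint would explain it.** This cannot be excluded. F = 8.741, one digit different, gives p = 0.0046 on (1, 55) df; p = 0.0049 in place of 0.0046 would fit F = 8.141 on 165 to 171 df. A misprint would still need correcting.

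**The global file holds more than 171 values.** True: across the three measures it holds 57 x (3 + 3 + 2) = 456. A model pooling MGI and plaque would have 342 values and about 330 error df, which gives 0.0046. That would not be a test of global MGI alone.

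**The patient set may differ.** The ANCOVA has 51 df, which suggests about 54 patients, and Table 1 lists 27 + 26 = 53. A different N could produce a different F, so Table 2 alone does not show that another kind of test was used. No patient count in the documents, however, brings the error df near 281.

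**A stronger reading is tempting.** A reader might infer that implant and non-implant averages were analysed as independent rows: 53 x 2 x 3 = 318 rows, with about 312 to 314 error df, gives 0.0046. The documents do not support stating this as fact. It is one of several fits, and a residual df of that size would not by itself show that within-patient correlation was ignored.

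**An equivalent test is already reported.** Also true. Table 2 gives a contrast of the planned type, on the planned unit, with a smaller p. That limits the consequence but leaves two conflicting figures for the same outcome.

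**Conclusion.** The point holds as an inconsistency in a reported primary-outcome result. As printed, F = 8.141, df = 1 and p = 0.0046 cannot all be right for a model of the global MGI scores: the p-value needs about 281 to 404 error df and at most 171 values exist. The result also differs from the matching contrast in Table 2. This rests on reading the printed df as the numerator df and on 57 patients, the largest N in the documents.

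The cause is undetermined. A misprint, a different patient set, a pooled-measure model, or site-by-visit rows analysed without allowing for repeated measurement are all possible.

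The size is modest. On the printed F values, p runs from 0.0012 (Table 2) to 0.0061 (F = 8.141 on 55 df), so significance at 0.05 does not reverse. Nor does the p of about 0.13 in the working show that the effect is absent: it combines percentages from one place with an error term from another, and those percentages may come from other patients or have been averaged differently. It shows only that the sentence needs reconciling. What changes is how strong the result is said to be, and whether it can be traced.

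**What to change.** Re-run the planned treatment-by-time model on global MGI with visits nested in patient. State the effect tested, N, and the numerator and denominator df, and say explicitly whether the test is the linear-time contrast or the overall interaction. Add the Day 90 between-group contrast with its 95% CI.

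Reconcile the result with Table 2 and with the 27.3% and 20.4% reductions, stating how and in which patients those were computed. Then replace or delete F = 8.141, p = 0.0046. If it came from a different data set or model, label it as such.

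The cost is one model re-run and a corrected sentence; no new data are needed. The p-value may move in either direction, since Table 2 is already more favourable than the quoted figure.

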Transformed Variable: Average outcomes					
Source	Type III Sum of Squares	df	Mean Square	F	Sig.
Intercept	2790.339	1	2790.339	9371.807	0.000
Implant	2.916	1	2.916	9.793	0.002
Measure	13.625	1	13.625	45.761	0.000
Group	1.954	1	1.954	6.562	0.011
Implant * measure	7.58	1	7.58	25.459	0.000
Implant * group	0.018	1	0.018	0.061	0.805
Measure * group	8.331	1	8.331	27.981	0.000
Implant * measure * group	16.127	1	16.127	54.166	0.000
Error	60.738	204	0.298		

Implants and Probing depth

Probing depth scores (PDS) were only collected at initial and last observations visits 1 and 4. At intake, control group (Group A) patients had significantly higher levels of probing depth around implanted teeth (mean = 2.93, SEM = 0.094) than in non-implanted teeth (2.69, 0.063), with $t = 2.31$, $df = 53$, $p = 0.025$. In addition, control group (Group A) implant site probing depth was greater at intake than for test group (Group X) probing depth at implanted sites, 3.40 (0.109) versus 2.45 (0.080) respectively, with $t = 7.07$, $df = 52$, $p < 0.001$.

[figure not shown]
Table 5 represents the results in an overall test of significance with PDS as a dependent variable. There were two notable interactions. One was a time by group interaction, representing that probing depths changed significantly differently over time. Another was a three-way interaction time-by-implant-by-group assignment. The time-by-group interaction was seen before in the PDS score and while significant, the actual difference was less than 1%. The three-way interaction is a false signal in that implant scores probe scores increased slightly in the test group (Group X) and decreased slightly in the control group (Group A) – and neither change was significant.

Probing depth scores for implant and non-implant sites did not change significantly in both groups did not change significantly in both implant and non-implant sites as observed over time for both groups. Figure 8 illustrates the lack of change in implant and non-implant depth scores in either group.

Table 5. Summary results of general linear model of probing depth measures for implant sites over time.

Tests of Within-Subjects Contrasts					
Measure: GGI					
Source	Type III Sum of Squares	df	Mean Square	F	Sig.
Time	15.113	1	15.113	563.159	0.000
Time * implant	1.507	1	1.507	56.172	0.000
Time * group	0.941	1	0.941	35.047	0.000
Time * implant * group	0.001	1	0.001	0.041	0.840
Error(Time)	2.737	102	0.027		

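### Table 4 is presented as the omnibus test of three outcomes, but it is MGI and plaque stacked together, without probing depth or a time term, and cannot support the efficacy statements that follow it

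*Combined protocol and SAP*

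**What the plan says.** Section [11] Statistical Evaluation sets out a "repeated measures analysis of variance on three primary outcomes: probing depth, gingival index, and plaque" and names the treatment-by-time interaction as the primary hypothesis.

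In the Results, under *Differential Effects of Mouthwashes on Implants*, the text states: "Table 4 illustrates the overall study results of treatments and implants on the three outcomes". It then makes three statements: probing depth did not differ between treatments at implant or non-implant sites; plaque and gingival index improved significantly under the test rinse; and implant sites improved faster under that rinse. Details are referred to Tables 5, 6 and 7.

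The relevant rows of Table 4 (source, Type III SS, df, mean square, F, p) include:
- "Measure 13.625 1 13.625 45.761 0.000"
- "Group 1.954 1 1.954 6.562 0.011"
- "Implant * group 0.018 1 0.018 0.061 0.805"

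The error row is 60.738 on 204 df, mean square 0.298. No row involves time.

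**The concern.** A factor indexing three outcomes has 2 df; Measure has 1. So at most two outcomes are in a table described as covering three, and the document does not say which. If probing depth was left out, the probing depth statement that follows has no basis in this table. If the rows compare average levels rather than changes, nothing in the table speaks to improvement or speed of improvement. And if two indices on different scales were pooled, a single Group or Implant*group p-value may describe neither of them. At stake is whether the table called the overall study result supports the site-level efficacy claims placed directly after it.

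**Working it through.** **1. Reproduce the printed figure.** Group F = 1.954 / (60.738/204) = 1.954 / 0.2977 = 6.563, p = 0.0111 on 1 and 204 df. Table 4 prints 6.562 and 0.011.

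**2. Identify the contents.** If two outcomes from the same design are stacked with a two-level Measure factor, each single-outcome SS divides between an effect and its interaction with Measure, and the error terms add.

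| Row | Table 6 (MGI) + Table 7 (plaque) | Table 4, effect + effect by Measure |
|---|---|---|
| Intercept | 1207.001 + 1596.963 = 2803.964 | 2790.339 + 13.625 = 2803.964 |
| Implant | 9.949 + 0.547 = 10.496 | 2.916 + 7.58 = 10.496 |
| Group | 9.177 + 1.108 = 10.285 | 1.954 + 8.331 = 10.285 |
| Implant*group | 8.613 + 7.532 = 16.145 | 0.018 + 16.127 = 16.145 |
| Error SS | 11.118 + 49.62 = 60.738 | 60.738 |
| Error df | 102 + 102 = 204 | 204 |

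Everything agrees to three decimals. Nothing is left over for probing depth.

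**3. Error term.** The error variances are 11.118/102 = 0.109 and 49.62/102 = 0.486, a ratio of about 4.5. Table 4 uses their mean, 0.298, which describes neither index. Table 1 has 27 + 26 = 53 patients. Two site types give 106 rows, and 106 − 4 cells = 102. Two measures give 212 rows, and 212 − 8 cells = 204. The error df therefore count a patient's two site averages and two indices as independent units.

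**4. Relative signs.** With e the signed square root of each single-outcome SS, the effect SS is (e₁ + e₂)²/2.
- Group: roots 3.03 and 1.05. Same sign gives 8.331, opposite sign 1.954. Printed: 1.954.
- Implant*group: roots 2.93 and 2.74. Same sign gives 16.127, opposite sign 0.018. Printed: 0.018.

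So MGI and plaque point in opposite directions in both rows. Taken separately, Implant*group is F = 79.0 for MGI and 15.5 for plaque (p = 0.00015); stacked, it is p = 0.805.

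**5. Direction and size.** The sums of squares do not say which arm is higher. Table 1 and the text on Figure 9 do: MGI is higher in the test group. The reverse sign would need test-arm implant MGI to average about 1.4 below control at the two later visits: (3 × −0.669 − 0.76)/2 = −1.38, where 0.669 is the implant difference implied by Table 6. That conflicts with the reported implant decreases of 26% and 19%. Even the 83% and 57% given in the same paragraph leave 2.82 × 0.17 − 2.06 × 0.43 = −0.41 at the last visit.

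Assuming 106 rows and three visits (318 values per index), a difference is 2√(SS/318):
- MGI: 2√(9.177/318) = +0.340
- Plaque: 2√(1.108/318) = 0.118, opposite sign, so −0.118
- Average: (0.340 − 0.118)/2 = +0.111, matching 2√(1.954/636) = 0.111 from Table 4

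The site-by-arm contrasts, 4√(SS/318), are +0.658 for MGI and −0.616 for plaque, which average 0.021. On the same assumption the intercepts give means of 1.95 and 2.24. Those are plausible score levels, not slopes or changes.

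**6. Baseline share.** From Table 1, test minus control:
- MGI: implants 0.76, other teeth 0.14; mean 0.45, contrast +0.62
- Plaque: implants 0.07, other teeth 0.67; mean 0.37, contrast −0.60

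The pooled baseline difference is (0.45 + 0.37)/2 = 0.41. The two later visits then average (3 × 0.111 − 0.41)/2 = −0.04. Both contrasts were already close to their Table 4 size before any rinse was used.

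**7. Table 5.** It is captioned as probing depth but labelled GGI. The accompanying text describes a notable three-way interaction; the printed row has p = 0.840. Treating Time as a normalised first-to-last contrast on 106 rows, the mean fall is √(2 × 15.113/106) = 0.534 and the arm difference is 2√(2 × 0.941/106) = 0.266. The falls are then 0.667 (test) and 0.401 (control), or 27.6% and 20.4% of the Table 1 MGI means of 2.415 and 1.965. The global gingival index reductions are reported as 27.3% and 20.4%. The label GGI is therefore credible, which leaves no printed implant-level model for probing depth.

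**The case against.** Several points on the other side stand. Table 4 prints highly significant Measure*group (F = 27.981) and Implant*measure*group (F = 54.166) rows, so an attentive reader can see that the effects differ by index, and Tables 6 and 7 report each index separately. No sentence cites Table 4's Group p-value as efficacy evidence; the p = 0.011 under *Global Plaque Score* is a different test. The Conclusions rest on ANCOVA, difference scores and slopes, which do not use Table 4. Table 2 already tests the slope of each outcome, probing depth included, at global level. The documents also say openly that probing depth was not measured at the second visit.

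A reader might infer from the Group row that the test rinse did worse. The documents do not support that. The row includes baseline, when the test arm was already 0.41 higher on the pooled scale, and the implied difference after baseline is about −0.04. A reader might equally take p = 0.011 as support for the rinse; that fails for the same reason. Nor are the two opposing site-by-arm contrasts treatment effects that the table conceals, since Table 1 shows them at nearly full size before treatment.

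None of this repairs the description of the table, or its use to introduce statements on probing depth, improvement and speed of response at implant sites.

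**Conclusion.** The point holds as a fault of labelling and interpretation. That Table 4 consists of MGI and plaque only, and that their Group and Implant*group effects oppose each other, follows exactly from the printed sums of squares and needs no assumption. That the test arm is the higher one rests on Table 1 and the Figure 9 text. The size of about 0.11 index points also assumes 53 patients and three visits; the error df agree with 53, although counts of 54, 56 and 57 appear elsewhere in the document. The 0.11 mainly reflects baseline imbalance and is evidence of neither benefit nor harm.

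Table 4 cannot support the statements that probing depth did not differ by site, that plaque and MGI improved, or that implant sites improved faster. This does not show those statements to be false; it shows that they must rest on other analyses, and for probing depth at implant level no model is printed.

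**What to change.** - Withdraw Table 4 and its introductory sentence, or retitle it *MGI and plaque levels averaged over visits* and cite no efficacy result from it.
- For implant and non-implant sites, report the time-by-group estimate for each outcome on its own scale, with a confidence interval and with rows from the same patient treated as correlated. Adjust for baseline where the arms were imbalanced.
- Include a probing depth model, correctly labelled, and correct the caption or the content of Table 5.
- State that probing depth was in no omnibus test.

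The cost is one table, a few sentences and a re-run of site-level models on data already held. What is lost is a single overall p-value that could not be interpreted.
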